4.4.2 Prohibited Therapy

Use of the following therapies is prohibited during the study:

- Any concomitant therapy intended for the treatment of solid tumors, either approved by health authorities or experimental, including chemotherapy, radiotherapy (except as noted in Permitted Therapy, Section 4.4.1), hormonal therapy, immunotherapy, biologic therapy, or herbal therapy
- Traditional herbal or homeopathic or natural medicines
 - Ingredients for such medicines have not been fully studied, and their use may result in unanticipated drug-drug interactions that may cause or confound assessment of toxicity.

Patients who require the use of any of these agents will be discontinued from study drug and followed for safety outcomes for 30 days after the last dose of study drug or until initiation of another subsequent anti-cancer therapy, whichever comes first. These patients will also continue to be followed for survival.

In vitro data demonstrates that cobimetinib is metabolized by CYP3A4. A clinical drug-drug interaction study with a strong CYP3A inhibitor showed a 6.6-fold increase in cobimetinib AUC. Thus, it is likely that exposures of cobimetinib will be significantly lowered in the presence of strong CYP3A inducers. The medications listed below should be avoided. If use of one of these medications is necessary, the risks and benefits should be discussed with the Medical Monitor prior to concomitant administration with cobimetinib.

- Strong CYP3A inducers, including but not limited to rifampin, carbamazepine, rifapentine, phenytoin, phenobarbital, and St. John's wort or hyperforin
- Strong CYP3A inhibitors, including but not limited to atazanavir, clarithromycin, erythromycin, indinavir, itraconazole, ketoconazole, nefazodone, nelfinavir, ritonavir, saquinavir, telithromycin, troleandomycin, and voriconazole

- Strong and moderate CYP3A inducers and inhibitors (as defined in [Appendix 11](#)) are prohibited for patients in the dose escalation stage during the DLT assessment window

Outside the DLT assessment window in the dose escalation stage, moderate CYP3A inhibitors and inducers are to be used with caution while strong CYP3A inducers and inhibitors should be avoided.

Caution should be use with concomitant medications that increase the risk of bleeding (including antiplatelet or anticoagulant therapy).

The above lists of medications are not necessarily comprehensive. Thus, the investigator should consult the prescribing information for any concomitant medication. In addition, the investigator should contact the Medical Monitor if questions arise regarding medications not listed above.

4.4.3 Prohibited Food and Supplements

Given the significant effect of CYP3A inducers and inhibitors on cobimetinib metabolism (described in Section 5.2 of the Investigator's Brochure), use of the following foods is prohibited during the study and for at least 7 days prior to the initiation of study treatment, unless otherwise specified below:

- St. John's wort or hyperforin (potent CYP3A inducer)
- Grapefruit juice (potent CYP3A enzyme inhibitors)

Ingestions of prohibited foods and supplements will render the patient non-evaluable for DLTs and may warrant removal from protocol therapy. Such ingestions must be reported to the Medical Monitor for determination of whether study drug may be continued. Patients who are discontinued from study treatment for this reason will be followed for safety outcome for 4 weeks after the last dose of study treatment or until initiation of another subsequent anti-cancer therapy, whichever comes first. These patients will also continue to be followed for survival.

4.5 STUDY ASSESSMENTS

Please see [Appendix 1](#) and [Appendix 2](#) for the schedules of assessments and schedule of PK assessments performed during the study.

4.5.1 Informed Consent Forms and Screening Log

Written informed consent for participation in the study must be obtained before any study-specific screening tests or evaluations are performed from the patient or parent/legal guardian. Informed Consent Forms and Child's Informed Assent Forms for enrolled patients and for patients who are not subsequently enrolled will be maintained at the study site.

All screening evaluations must be completed and reviewed to confirm that patients meet all eligibility criteria before enrollment. The investigator will maintain a screening log to record details of all patients screened and to confirm eligibility or record reasons for screening failure, as applicable.

4.5.2 Medical History and Demographic Data

Medical history includes clinically significant diseases, major surgeries, cancer history (including prior cancer therapies and procedures), menstrual history, fertility history, and puberty history. In addition, all medications (e.g., prescription drugs, over-the-counter drugs, herbal or homeopathic remedies, nutritional supplements) used by the patient within 7 days prior to initiation of study drug will be recorded.

Demographic data will include age, sex, and self-reported race/ethnicity where permitted by health authorities.

4.5.3 Physical Examinations and Assessments

A complete physical examination should include an evaluation of the head, eyes, ears, nose, and throat, and the cardiovascular, dermatological, musculoskeletal, respiratory, gastrointestinal, genitourinary, and neurological systems. Any abnormality identified at baseline should be recorded on the General Medical History and Baseline Conditions eCRF.

At subsequent visits (or as clinically indicated), changes from baseline abnormalities should be recorded in the source documents. New or worsened clinically significant abnormalities should be recorded as adverse events on the Adverse Event eCRF.

When age appropriate, patients will be asked specifically about vision changes as part of each physical examination in addition to interval medical history.

During the treatment period, weight will be measured within 3 days prior to Day 1 dose of each cycle. During the follow-up period, weight should be measured every 3 months for the first 2 years, every 6 months during the third year, and yearly thereafter until end of study (Section 3.2).

During the treatment period, height, head circumference (until 3 years of age), and Tanner stage should be measured every four cycles (approximately every 3 months). During the follow-up period, height, head circumference, and Tanner stage should be measured every 3 months for the first 2 years, every 6 months during the third year, and yearly thereafter until end of study (Section 3.2). Tanner staging and height should be performed until the patient has reached Tanner Stage V.

4.5.4 Vital Signs

Vital signs will include measurements of respiratory rate, pulse rate, systolic and diastolic blood pressures, oxygen saturation, and temperature.

4.5.5 Tumor and Response Evaluations

All known sites of disease must be documented at screening and re-assessed at each subsequent tumor evaluation. Full baseline tumor assessments should be performed within 28 days prior to initiation of study drug (Day 1 of Cycle 1). Baseline assessments will consist of the entire diagnostic workup consistent with the response evaluation system used for the specific tumor type. Tumor assessments must be performed during the last week of the even-numbered cycles (i.e., at the end of Cycles 2, 4, 6, 8, etc., prior to the start of treatment in the next cycle). *For patients who have not met study criteria for progressive disease after 12 cycles, subsequent response assessments should be conducted at Cycles 16, 20, 24, and every 6 cycles thereafter.* At the investigator's discretion, tumor assessments may be repeated at any time if disease progression is suspected.

Response will be assessed by the investigator on the basis of physical examinations, computed tomography (CT) scans or MRI scans and additional ¹²³I-MIBG imaging for neuroblastoma patients. The following response assessment systems will be used mINRC, RANO criteria for HGG, RANO criteria for LGG, or RECIST v1.1, as appropriate for the patient's diagnosis. CT or MRI scans should evaluate neck, chest, abdomen, and pelvic region if clinically indicated. MIBG scanning should be used for response assessments in neuroblastoma patients, if positive at baseline. PET scans may be performed at the discretion of the treating physician.

Any objective response must be confirmed by repeat assessments ≥ 4 weeks after initial documentation. The same radiographic procedure used to assess disease sites at screening should be used throughout the study (e.g., the same contrast protocol for CT scans). To the extent that is feasible, assessments should be performed by the same evaluator to ensure internal consistency across visits.

Patients with neuroblastoma must have a MIBG scan and bilateral bone marrow aspirates and biopsies done for disease evaluation. If the enrollment bone marrow aspirates and biopsies are negative for disease, subsequent bone marrow aspirates and biopsies are not needed. Patients with neuroblastoma should also have urine catecholamines (including homovanillic acid and vanillylmandelic acid) sent at screening and with all responses assessments.

Patients without neuroblastoma who have a clinical suspicion of bone marrow involvement should also have bilateral bone marrow aspirates and biopsies performed at screening. Those with positive bone marrow involvement at screening should then have bilateral bone marrow aspirates and biopsies done with each disease reassessment until the second consecutive negative biopsy.

4.5.6 Ophthalmologic Examinations

All patients will undergo ophthalmologic examinations, performed by a qualified ophthalmologist, at specified timepoints throughout the study (see [Appendix 1](#)). *For patients who have completed 6 cycles of cobimetinib therapy and who have not developed serous retinopathy, retinal detachment, or other adverse events involving the retina, ophthalmologic evaluations will be performed at Cycles 8, 10, 12, 16, 20, 24, and every 6 cycles thereafter.*

Patients will be evaluated at screening for history or evidence of retinal pathology that is considered to be a risk factor for or indicative of neurosensory retinal detachment, CSCR, neovascular retinopathy, or retinopathy of prematurity.

Ophthalmologic examinations will include age-specific visual acuity testing (*which should be reported in Snellen units*), intraocular pressure measurements, slit-lamp ophthalmoscopy, and spectral domain optical coherence tomography (OCT) at baseline, the beginning of every cycle, study drug discontinuation, and at other timepoints identified in the protocol. Indirect ophthalmoscopy and color fundus photography will be required only at baseline and at study drug discontinuation. If spectral domain OCT is not available, time domain OCT may be performed. In patients who are unable to successfully complete OCT scans due to underlying visual impairment from non-retinal causes (such as brain tumor), color fundus photography and indirect ophthalmoscopy should be performed instead of OCT at each scheduled ophthalmologic evaluation. Additionally, fluorescein angiography will be performed for identified OCT serous fluid accumulation or edema and thereafter based upon clinical findings. Binocular indirect ophthalmoscopy will be performed any time fluorescein angiography is performed. Fluorescein angiography may be deferred if patients have known contrast allergies or abnormal renal function, at the discretion of the investigator. Providers should be advised that patients <3 years of age are likely to require examination under anesthesia for successful evaluation.

4.5.7 Cardiac Function Monitoring

Cardiac echocardiograms or MUGA will be performed during screening to assess baseline cardiac function and at regular intervals beginning with the visit at Cycle 2. These exams will be repeated every third cycle thereafter (i.e., Cycles 5, 8, 11, etc.) and at the end of study visit.

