3.1.1 Dose-Escalation Stage

Cohorts of 3–6 pediatric patients each will be treated at escalating doses of cobimetinib in accordance with the dose-escalation rules described below. The first patient at each dose level must complete at least 5 days of treatment (Days 1–5 of Cycle 1) without a DLT (as defined in Section 3.1.1.1) before subsequent patients can be treated at the same dose level.

The DLT assessment window is defined as Days 1–28 of Cycle 1. Adverse events identified as DLTs, as defined below (see Section 3.1.1.1), will be reported to the Sponsor within 24 hours (see Section 5.4.2).

[figure not shown]
Two formulations will be available for the protocol: a tablet (20 mg) and a suspension (4.8 mg/mL). An MTD or MAD will initially be determined for tablets in patients 6 years and above. Once the MTD or MAD is identified for tablets, enrollment of patients using the suspension will commence following review of relevant data from the tablet dose escalation. The starting dose for the suspension will be a minimum of one dose level below the MTD or MAD of the tablets (see Section 3.1.1.2 for age requirements for suspension). Additional dose escalation with the suspension may proceed according to the dose escalation rules (Section 3.1.1.2) until an MTD or MAD is identified for the suspension. On the basis of an ongoing review of safety data and available PK data, increases in dose level or continued enrollment for either formulation may be halted by the Sponsor as deemed appropriate.

Patients who discontinue from the study prior to completing the DLT assessment window for reasons other than a DLT will be considered non-evaluable for dose-escalation decisions and MTD or MAD assessments. These patients will be replaced at that same dose level unless there are 3 or more patients already treated and all were evaluated with no DLT at that level. Patients who miss five or more doses (i.e., > 18% of the cumulative dose) during the DLT assessment window for reasons other than toxicity will also be replaced. Patients who ingest moderate or strong CYP3A inducers or inhibitors (defined in Appendix 11), ingest prohibited foods/supplements (defined in Section 4.4.3), or receive supportive care during the DLT assessment window that confounds the evaluation of DLTs (not including supportive care described below as part of the DLT definition) may be replaced at the discretion of the Medical Monitor.

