3.1.1.1 Definition of Dose-Limiting Toxicity

Any one of the following events will be considered a DLT if it occurs during the DLT assessment window and is assessed by the investigator to be related or possibly related to cobimetinib (rules for attributing causality are defined in Section 5.3.4):

- Grade ≥ 4 neutropenia (ANC $< 0.5 \times 10^9/L$) lasting > 7 days
- Grade ≥ 4 neutropenia with documented infection
- Febrile neutropenia, defined as ANC $< 500/mm^3$ with a single temperature of $> 38.3^\circ C$ ($101^\circ F$) or a sustained temperature of $\geq 38^\circ C$ ($100.4^\circ F$) for more than 1 hour
- Grade ≥ 4 (i.e., life threatening) anemia of any duration

- Grade ≥ 4 thrombocytopenia lasting > 48 hours or any thrombocytopenia requiring a platelet transfusion, with the following exception:
 - For patients who have undergone autologous stem cell transplant or ^{131}I -metaiodobenzylguanidine (MIBG) therapy, Grade ≥ 4 thrombocytopenia lasting > 7 days or any thrombocytopenia requiring a platelet transfusion on two or more separate dates will be considered a DLT.
- Grade ≥ 3 thrombocytopenia with bleeding
- Elevation of serum hepatic transaminase (ALT or AST) $\geq 5 \times$ the upper limit of normal (ULN)
 - For patients with elevated hepatic transaminase levels at baseline as a result of liver metastases, hepatic transaminase $\geq 5 \times$ baseline and $< 10 \times$ baseline for > 3 days, or any hepatic transaminase $\geq 10 \times$ baseline, will be considered a DLT.
- Elevation of serum bilirubin $\geq 3 \times$ ULN
- For patients reliably able to report visual symptoms: Grade ≥ 2 visual disturbance that does not resolve to Grade ≤ 1 within 72 hours after interruption of cobimetinib treatment
- Retinal pathology of any grade, or Grade ≥ 2 uveitis or iritis
- Grade ≥ 2 hemorrhage of any type
- Intracranial hemorrhage of any grade
- Grade ≥ 4 CPK elevation
- Rhabdomyolysis of any grade
 - Rhabdomyolysis includes elevations of CPK in conjunction with either clinical features (such as muscle pain, signs of renal failure, dark red or brown urine) or with laboratory evidence of renal insufficiency (including Grade 2 or higher increased creatinine or creatinine clearance [or radioisotope glomerular filtration rate] < 70 mL/min/1.73 m²), or investigator judgment that a clinical scenario is consistent with rhabdomyolysis.
- Grade ≥ 2 ventricular dysfunction or symptomatic congestive heart failure

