- Reduction in left ventricular ejection fraction (LVEF) below 50% (or shortening fraction below 28%) AND either symptomatic heart failure or a $\geq 10\%$ relative reduction from baseline measurement
 - Note: The relative reduction must be $\geq 10\%$ of baseline function, not an absolute decrease of ≥ 10 percentage points.
- Grade ≥ 4 (i.e., life threatening) vomiting or diarrhea of any duration

- Grade ≥ 3 non-hematologic, non-hepatic, non-ocular adverse event, with the following exceptions, which will not be considered DLTs:
 - Grade ≥ 3 diarrhea or rash that resolves to Grade ≤ 2 within 7 days after interruption of cobimetinib treatment.
 - Grade 3 fever.
 - Grade 3 mucositis or stomatitis that resolves to Grade ≤ 2 within 3 days.
 - Grade ≥ 3 nausea or vomiting that responds to standard-of-care therapy within 3 days.
 - Grade 3 fatigue lasting ≤ 3 days.
 - Grade 3 laboratory abnormalities that are asymptomatic and considered by the investigator not to be clinically significant.

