In order to minimize safety risks during dose escalation but to ensure optimal access for children to the trial, dose escalation will commence according to the rolling 6 design. In this design, up to a maximum of 6 patients can be enrolled concomitantly at the same dose level. The dose level allocated to a new patient is based on the number of patients currently enrolled and evaluated, the number of patients experiencing DLT, and the number of patients whose evaluation is pending at the time of new patient entry. De-escalation occurs when two or more DLTs occur at a dose level, whereas escalation can be performed when 3/3, 4/4, 5/5, 5/6, or 6/6 patients are evaluated without a DLT. Otherwise, patients can be included at the same level up to a total of 6 patients per dose level. Dose escalation will proceed according to the rules shown in [Table 1](#) (adapted from Doussau et al. 2012 and Skolnik et al. 2008).

Table 1 Dose Determination for the Next Patient in Rolling 6 Design

Number of Patients Enrolled	Number of Patients with DLTs	Number of Patients without DLT	Number of Patients with Data Pending	Enrolling Dose Level (MTD Not Exceeded)	Enrolling Dose Level (MTD Previously Exceeded)
2	0,1	Any	Any	Same	
2	2	0	0	Dose decrease	
3	0	0,1,2	3,2,1	Same	
3	0	3	0	Dose increase	
3	1	0,1,2	2,1,0	Same	
3	≥2	Any	Any	Dose decrease	
4	0	0,1,2,3	4,3,2,1	Same	Same
4	0	4	0	Dose increase	Same
4	1	0,1,2,3	3,2,1,0	Same	Same
4	≥ 2	Any	Any	Dose decrease	Dose decrease
5	0	0,1,2,3,4	5,4,3,2,1	Same	Same
5	0	5	0	Dose increase	Same
5	1	0,1,2,3,4	4,3,2,1,0	Same	Same
5	≥2	Any	Any	Dose decrease	Dose decrease
6	0	0,1,2,3,4	6,5,4,3,2	Suspend	Suspend
6	0	5,6	1,0	Dose increase	MTD
6	1	0,1,2,3,4	5,4,3,2,1	Suspend	Suspend
6	1	5	0	Dose increase	MTD
6	≥2	Any	Any	Dose decrease	Dose decrease

MTD=maximum tolerated dose.

Notes: Same=next patient would be treated at the same dose.

Dose increase=next patient would be treated at a higher dose.

Dose decrease=next patient would be treated at a lower dose.

Suspend=enrollment will be suspended until enough patients have been evaluated.

Dose escalation will proceed according to [Table 1](#) and in accordance with the rules listed below.

- If 2 or more of the first 6 DLT-evaluable patients in a cohort experience a DLT, the MTD will have been exceeded; subsequent patients must be treated at a lower dose level.

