Decrease in cardiac function has been identified as an adverse event that falls under “Warnings and Precautions” for adult use of cobimetinib. Study GO28141 demonstrated a decrease in cardiac function in 7% of cobimetinib plus vemurafenib-treated patients versus 3% of vemurafenib-treated patients. Most cases were asymptomatic. Symptoms consistently improved following treatment discontinuation, treatment interruption, or dose reduction in the cobimetinib arm, while improvement was inconsistent in the vemurafenib arm. There has been no in vitro or nonclinical evidence of decreased cardiac function with cobimetinib administration.

As there is no biomarker that can accurately identify early decreased cardiac function in children, cardiac function will be assessed through echocardiograms performed at specified timepoints throughout the study (see [Appendix 1](#)). This is particularly important in pediatric patients who have been treated with an anthracycline analogue, and even more so in pediatric patients who have had chest radiotherapy in addition to anthracycline treatment, both of which increase the risk of cardiac dysfunction.

Guidelines for the management of symptomatic reduction in left ventricular ejection fraction are provided in [Table 3](#).

Table 3 Guidelines for Management of Asymptomatic Reduction in Left Ventricular Ejection Fraction

Patient	LVEF Value	Recommended Cobimetinib Dose Modification	LVEF Value Following Treatment Break	Recommended Cobimetinib Daily Dose
Asymptomatic	≥ 50% (or 40%–49% and < 10% absolute decrease from baseline)	Continue at current dose	N/A	N/A
	< 40% (or 40%–49% and ≥ 10% absolute decrease from baseline)	Interrupt treatment for 2 weeks	< 10% absolute decrease from baseline	1 st occurrence: reduce by 1 dose level
				2 nd occurrence: reduce by additional dose level
				3 rd occurrence: permanent discontinuation
< 40% (or ≥ 10% absolute decrease from baseline)			Permanent discontinuation	

LVEF=left ventricular ejection fraction; FS=fractional shortening.

Note: Investigators may substitute FS for LVEF in algorithm above as follows:

- FS ≥ 28% equivalent to LVEF 50%
- FS 25%–27.9% equivalent to LVEF 40%–49%
- FS < 25% equivalent to LVEF < 40%

Patients who require dose reduction should have LVEF measurements at 2, 4, 10, and 16 weeks after diagnosis. Patients with symptomatic heart failure must discontinue study drug.

Rhabdomyolysis and CPK Elevations

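### In dose escalation, the asymptomatic LVEF criterion for a DLT has no required on-treatment scan inside the Day 1–28 window, and scoring of findings on Days 29–32 is not defined

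*Combined protocol and SAP*

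**What the plan says.** Section 3.1.1 fixes the window: "The DLT assessment window is defined as Days 1–28 of Cycle 1". Under Section 3.1.1.1 an event "will be considered a DLT if it occurs during the DLT assessment window" and is judged at least possibly related to cobimetinib.

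Two of the listed criteria can be met by a patient with no symptoms:

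- **Cardiac:** LVEF below 50%, or shortening fraction below 28%, together with a relative fall of at least 10% from baseline. Symptomatic heart failure is a separate route.
- **Eye:** "Retinal pathology of any grade".

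The tests that would show them are scheduled as follows:

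- **Echo/MUGA:** at screening, then "at regular intervals beginning with the visit at Cycle 2" (Section 4.5.7; Appendix 1, footnote z). None is scheduled in Cycle 1.
- **Eye examination:** Cycle 1 Days 8 and 15, then the start of Cycle 2 (Appendix 1, footnote bb).
- **Visit window:** 3 days either side, with assessments done before dosing on treatment days (Appendix 1, Notes).
- **Dosing:** none on Days 22–28 (Section 4.3.2).

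Section 3.1.1.2 allows escalation on the count of patients free of DLT: "escalation can be performed when 3/3, 4/4, 5/5, 5/6, or 6/6 patients are evaluated without a DLT". The data to be reviewed first are demographic, adverse event, laboratory, dosing and available PK data. The Cycle 2 echo and eye results are not named.

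**The concern.** A criterion that only imaging can reveal is in force for 28 days, and no imaging is required in those 28 days. Section 5.1.2.1 makes plain why imaging is needed: "there is no biomarker that can accurately identify early decreased cardiac function in children". It also reports from the adult Phase III trial "a decrease in cardiac function in 7% of cobimetinib plus vemurafenib-treated patients versus 3% of vemurafenib-treated patients. Most cases were asymptomatic". A patient can therefore be entered in Table 1 as free of DLT although the asymptomatic LVEF criterion was never tested.

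For the retina the gap is narrower: two examinations fall inside the window and only its last part is uncovered. Section 5.1.2.1 says about half of the serous retinopathy events in the adult trial were asymptomatic Grade 1. Questions about vision at physical examinations would not find those.

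The scoring gap adds to this. The same finding counts if the Cycle 2 visit happens to fall on Day 28 and has no stated status if it falls on Day 29. With 3 to 6 patients per dose level, one patient scored differently can change the decision. A missed DLT can only lower the count, so the error favours passing a dose.

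**Working it through.** The plan states no figure on this point, so there is none to reproduce. The check is calendar arithmetic, followed by an illustration on assumed rates.

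**Dates**

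- Cycle 2 Day 1 = 28 + 1 = Day 29. With 3 days either side, the visit may fall on Days 26–32. Three of those seven days (26–28) are inside the window and four (29–32) are outside.
- Required on-treatment echo/MUGA by Day 28: 0. One on Days 26–28 is permitted, not required.
- The Day 15 eye examination may fall on Days 12–18. Window days after it: 28 − 18 = 10 to 28 − 12 = 16. Dosing days after it: 21 − 18 = 3 to 21 − 12 = 9.

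**Who can be unexamined when the cohort is scored**

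- A patient's Cycle 2 examinations are due by that patient's own Day 32. When the last patient reaches Day 28, someone who started d days earlier is at Day 28 + d. That person has been examined if d ≥ 4 and Cycle 2 was started.
- The first patient at a dose level must complete 5 treatment days before others start (Section 3.1.1), so d is at least 5 and that patient is normally already examined.
- This leaves the last-enrolled patient, any who started fewer than 4 days before, and patients who complete Day 28 but stop for progression. With a last dose on Day 21, the discontinuation visit at 30 ± 3 days falls on Days 21 + 27 = 48 to 21 + 33 = 54, which is 20 to 26 days after the window closes. It is earlier, if possible, when another anti-cancer treatment starts sooner. The eye examination there can be waived (footnote cc).

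**Illustration (assumed rates)**

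Let the true DLT rate be p, and suppose a fraction δ of patients have a DLT that goes unscored, for the last of six patients only. Then

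P(≤1 of 6) = (1 − p)^5 + 5p(1 − p)^4 × (1 − p + δ).

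- p = 0.30: 0.168 + 0.360 × (0.70 + δ). For δ = 0, 0.01, 0.02, 0.04 this gives 42.0%, 42.4%, 42.7%, 43.5%.
- p = 0.40: 0.078 + 0.259 × (0.60 + δ). For δ = 0 and 0.04 this gives 23.3% and 24.4%.
- For 0 of 3 at p = 0.30: 0.49 × (0.70 + δ). For δ = 0 and 0.04 this gives 34.3% and 36.3%.

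The values of δ are assumptions. The documents give no paediatric or Cycle 1 rate for either criterion. The only cardiac rates are the adult ones above, 7% against 3%, on combination therapy and with no Cycle 1 breakdown.

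**The case against.** The best case on the other side is that the first echo comes right after Cycle 1, before re-dosing, and that this is a proportionate choice. Section 5.1.2.1 adds that symptoms consistently improved on stopping, interrupting or reducing treatment in the cobimetinib arm, and that there is no in vitro or nonclinical evidence of reduced cardiac function. The DLT test is when an event occurs, not when it is detected. Since no drug is given on Days 22–28, a pre-dose finding on Day 29 reflects Cycle 1 exposure and could be dated into the window. The Medical Monitor, investigators and Internal Monitoring Committee review data before escalation. The Sponsor may halt escalation. Serous retinopathy and Grade ≥ 2 LVEF reduction are reportable within 24 hours.

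Much of this stands and limits the size. It does not supply a scan inside the window or a stated scoring rule, and expedited reporting helps only once a finding has been made.

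A reader might infer three stronger things that the documents do not support:

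- **That the retinal criterion also goes untested.** It is examined twice in the window. Steady state is expected in about 8–10 days (Section 1.2.2.1), so even a Day 15 visit held on Day 12 falls at steady state.
- **That everyone who stops after Cycle 1 is unseen until about Day 48.** Section 4.6.2 keeps patients who stop for reasons other than progression on the on-treatment assessment schedule until progression, another treatment or withdrawal of consent.
- **That the whole cohort is under-scored.** Applying the assumed 4 points to all six patients at a true 30% rate would give 51%. That requires no finding on Days 29–32 ever to be scored for anyone, which the protocol does not say.

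**Conclusion.** The point holds as a minor gap in DLT ascertainment. The asymptomatic LVEF route has no required in-window test, late-window asymptomatic retinal onset can be missed, and the status of a pre-dose finding on Days 29–32 is left open. The schedule facts are certain.

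The size cannot be derived from the documents. It is probably small: 1.5 percentage points on P(≤1 of 6) under the assumption that only the last patient is affected, by 4 points at a true 30% rate. It would be larger if several patients started within a few days of the last one.

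The effect is confined to the DLT count and the MTD or MAD. The overall safety analysis still captures the events, and the expansion dose may be set below the MTD or MAD. The gap does not show that any dose would be wrongly declared tolerable.

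**What to change.** For dose-escalation patients only:

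1. Perform the already scheduled Cycle 2 echo/MUGA and eye examination in the off-drug week, preferably on Days 26–28, which the visit window already permits. Let them serve as the Cycle 2 examinations.
2. State in Section 3.1.1.1 that a qualifying finding first seen on Days 29–32, before the first Cycle 2 dose, counts as a DLT.
3. State there that these results are reviewed before the patient is scored as free of DLT.

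For a patient who completes Day 28 but will not start Cycle 2, do the examinations on those days where possible. If one is missing, flag it at the escalation review. This leaves a small residual gap, which is preferable to holding the cohort or replacing the patient.

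The cost is a few sentences of protocol text, with no extra patients and no extra procedures for those continuing to Cycle 2. The downsides are:

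- a narrower visit window for sites;
- a possible wait of up to about 4 days (Day 28 to Day 32) plus reading time if the examinations slip;
- a pre-Cycle 2 safety check done a few days before re-dosing;
- for the few who stop after Cycle 1, an eye examination that might otherwise have been waived. Section 4.5.6 expects this to need anesthesia in children under 3 years.
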